For the study's website, we will use shared server space provided by InMotion Hosting, Inc (website www.[name].com). We will be using AES-256-CBC encryption with SHAI for message authentication and RSA as the key exchange mechanism. The video recordings will be collected on devices that are FIPS-140-2 compliant. The data at rest at InMotion Hosting is AES-256 encrypted at rest, and the data being transferred are encrypted at transfer (AES-256). Data will be unencrypted only by study staff members who have access to the secured server at InMotion Hosting; the encryption key is held only by our staff. This will ensure all video uploads and data that the participant sends over the internet via their phones will only be transferred over encrypted network connections, essentially nullifying the possibility of someone gaining access to the video before it reaches our server. InMotion also runs audits regularly of the websites hosted within their shared servers to prevent scriptside vulnerabilities, as well as having a 24/7 support team monitoring their servers. The web application written for this study has been checked for SQL injection, Code Injection, XSS, and RFI vulnerabilities and has passed. The site will only be accessible by the study participants and the study coordinators via 512-bit SHA-2 hashed passwords.

In previous studies using this methodology that have been run in the Traumatic Stress and Health Research Laboratory, we have had no participant complaints regarding issues of privacy and confidentiality related to use of the smart phone videotaping procedures. As security controls have not been validated for InMotion Hosting, we will include a statement in the informed consent that the data/videos voluntarily submitted will be sent to InMotion and are no longer covered by Duke privacy protections.

No "key personnel outside Duke" will have access to identifying information on subjects. There will be only one key personnel member outside Duke. [name], the smart phone app developer and website developer/maintainer, will have access to coded data as he provides telephone and/or website

support. He will not have access to PHI. Data that links participants to information collected in the course of a given study will be kept separately from identifying information in an electronic, password-protected MS Access database stored at duhsnas-pri\dusom_psych\private\[name] Logs\Marijuana and Smoking; the key connecting identifying information and data will be stored here as well. Hard copy paper records will be stored in a locked filing cabinet in the study coordinator's locked office, within [name] laboratory space at Duke University Medical Center South. Information from the interview and/or questionnaires may be entered into a computerized database that will be stored on the DUMC server at duhsnas-pri\dusom_psych\private\[name] Logs\Marijuana and Smoking in a password-protected database separate from the "logbook" of identifying information. This database is accessible only by [name] and study staff. Any staff members who leave the study for any reason will have access to study resources, including data, removed immediately.

The study's safety monitoring plan is based on long-term clinical and research experience with patients with psychiatric illness, and is explained in more detail in the "Data and Safety Monitoring Plan" section. All project staff will complete educational units required by Duke's IRB, including CITI training and DHRT training.

Protection From Risk: Certificate of Confidentiality

In order for us to further protect the privacy of research participants, we have obtained a Certificate of Confidentiality (CoC) from the National Institutes of Health, certificate CC-DA-16-150. With this Certificate, we cannot be forced (for example by court subpoena) to disclose research information that may identify you in any Federal, State, or local civil, criminal, administrative, legislative, or other proceedings. Disclosure will be necessary, however, upon request of DHHS for audit or program evaluation purposes. Participants are informed in the informed consent process that study investigators will use the Certificate to resist any demands for information that would identify them, except as follows:

- 1. A CoC does not prevent the participant or a member of his/her family from voluntarily releasing information about the participant.
- 2. If an insurer or employer learns about a participant's participation, and obtains consent to receive research information, then we may not use the CoC to withhold this information.
- 3. If a participant reveals current intent to harm him/herself or someone else, we may be required to take action in accordance with our laboratory's existing Psychiatric Emergencies SOP.
- 4. If a participant reveals anything that gives cause to suspect abuse or neglect of any child, elderly adult, or person with a disability, we are required by federal law to report the suspected abuse to the local Department of Social Services.

Data and Safety Monitoring Plan

Quitting smoking and marijuana use should enhance rather than jeopardize health status, and potential serious adverse events (SAEs) for participants in this project are not expected. Regardless, we will minimize potential risk by careful screening of potential participants (e.g., medical clearance by their primary care provider if there are contraindications to smoking cessation pharmacotherapy).

The individuals responsible for data safety and monitoring will be the PI, the project manager, and the Study Physician. The Study Physician for this trial will be [name]., Ph.D. [name] is a board certified general psychiatrist, and is the treating physician of the local VA Medical Center's specialty smoking cessation clinic. As the Study Physician, [name] will ensure participants are medically cleared to participate in this trial and will review all reports of adverse events (AEs) sent by the study coordinator and evaluate the patient as necessary to determine whether there is any corrective action needed.

Further data safety and monitoring will be provided by the PI. There will be several ongoing mechanisms for monitoring and reporting of AEs: 1) ongoing participant contact via study personnel, 2) a toll-free number provided to participants to report concerns related to study participation; 3) weekly meetings between the PIs and study personnel.

The PI will meet at least weekly with study personnel to discuss participants' reactions to the intervention, proper delivery of the intervention, and any adverse events or unanticipated problems. Regular meetings between investigators and the project manager will allow for ongoing progress reports, including the number of participants currently involved in the study groups, attrition rates, and scheduled data collection from participants, as well as notification and review of any AEs. Safety monitoring for AEs will be conducted in real time by the PI and/or project manager. The following information about adverse events will be collected: 1) the onset and resolution of the AE, 2) an assessment of the severity or intensity (use existing grading scales whenever possible), 3) an assessment of the relationship of the event to the study (definitely, probably, possibly or not related), and 4) action taken (e.g., none, referral to physician, start or increase concomitant medication). The PI will determine the severity of the event, will assign attribution to the event, and will monitor the event until its resolution. Any adverse events will be reported to the IRB in accordance with the IRB guidelines.

Plans for Responding to a Participant Who Expresses Suicidal Ideation

Our research laboratory has established standards of practice for the evaluation of risk of suicide and homicide; these standards have been previously approved by the DUMC IRB. The policy includes a thorough risk assessment including evaluation of risk factors and protective factors associated with both suicide and homicide. Also included in the policy are differential recommendations for action based on determinations of low, moderate, or high risk. Any staff member conducting an interview in which moderate or high risk is determined will contact a senior staff person with clinical expertise in risk assessment.

Data Analyses

Descriptive statistics will be used to summarize all study variables. For continuous variables, means, standard deviations, percentiles, ranges, box plots and histograms will be generated. For categorical variables, frequencies and proportions will be generated. We will examine all variables to determine if parametric distributional assumptions (e.g. normality for the continuous variables) are valid. Variables not meeting distributional assumptions will either be transformed or modeled using nonparametric or

semi-parametric methods (e.g. quasi-likelihood methods; McCullagh & Nelder, 1989). In planning a full RCT of the tele-health mCM intervention for CUD and smoking, it is important to evaluate study feasibility and treatment procedures, as well as gaining information about effects on proposed outcome variables. To remain consistent with guidelines for designing and evaluating pilot studies, analyses will be primarily descriptive (Thabane et al., 2010) and aimed at informing feasibility and needed modifications rather than detecting statistically significant between-group differences (Leon, Davis, & Kraemer, 2011). However, to best utilize participant data to optimally design the treatment, we have established several objectives to indicate whether the planned trial is feasible.

Feasibility of cannabis abstinence assessment will be based on data from this pilot. While the validity of the Alere Oratect Oral Fluid Drug Screen Device has demonstrated excellent agreement with clinical samples analyzed with GC/MS methods, the utility of using daily saliva tests and CO (which measures carbon monoxide for cannabis smoking in the past 3 hours) has not been evaluated. We will examine the utility of the proposed saliva testing protocol. Additionally, qualitative data on the use of saliva tests will be examined to ensure that participants find it acceptable and preferable to in-clinic assessment methods.

The feasibility and acceptability of the multi-component tele-health mCM intervention will be assessed. We will collect frequency data regarding the number of videos transmitted, number of study measures completed at each time point, the amount of missing data (including missed videos), the number of sessions attended, and the frequency and severity of adverse events. We will assess the association of potential stratification variables (sociodemographic, psychiatric, and CUD/smoking severity variables) with feasibility indices, adherence to study protocol (video transmission, completion of study measures at each time point, session attendance), attrition, and adverse events. We will also determine whether attrition rates and frequency and severity of adverse events exceed those of previous smoking treatment trials. These data will provide important information useful in refining the intervention and associated assessments/procedures prior to their implementation in a larger-scale RCT.

References

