Our long-term goal is the reduction of morbidity associated with cannabis and smoking through the implementation of cost-effective, evidence-based interventions that maximize recovery. The purpose of this **pilot** project is to evaluate feasibility of treatment, recruitment, and abstinence bioverification methods for a combined cannabis and tobacco smoking tele-health mCM intervention that will effectively treat both disorders. Results from this pilot project will be used in support of an NIH grant to further develop the treatment and evaluate its feasibility and acceptability on a larger scale.

Preliminary Data

We developed and tested the mCM smoking app in combination with telephone CBT and used them in an initial validation study of 22 smokers with posttraumatic stress disorder (PTSD; Hertzberg et al., 2013). In this study, participants were randomized to 4 weeks of mCM plus CBT or to CBT plus yoked non-contingent reinforcement condition (i.e., compensation was based on earnings of participant matched from the other condition). Participant adherence to the protocol of submitting two on-time valid video readings daily was excellent (92%). Three-month self-reported 7-day point-prevalence quit rates were 18% in the yoked group and 50% in the mCM group. These preliminary results suggest that the tele-health mCM intervention is feasible and may lead to a longer duration of abstinence when CBT complements mCM in a multi-component intervention.

To further evaluate the tele-health mCM intervention, we enrolled 20 homeless smokers, and they all received the tele-health mCM intervention with CBT and standard smoking pharmacotherapy (Carpenter et al., 2015; Hertzberg et al., 2013). The majority of the sample (70%) had a history of CUD. Adherence to the timing and procedures for uploading videos with the mCM app was excellent during the treatment phase (93%). After 4 weeks of the tele-health mCM intervention, bioverified 7-day point-prevalence abstinence was 50%. Despite removing monetary compensation for abstinence at 4 weeks post-quit, bioverified abstinence in the tele-health mCM group was 55% at a 3-month follow-up assessment, and 45% at a 6-month follow-up assessment (Carpenter et al., 2015).

Methods

Participants

Up to 10 participants with CUD and smoking will be enrolled, with a goal of 5 participants completing the intervention.

Participants will be eligible for inclusion in the study if they meet the following criteria:

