- report 40 or more days of cannabis use in the past 90 day;
- have smoked at least seven cigarettes in the past seven days;
- have been smoking for at least the past year;
- can speak and write fluent conversational English;
- are between 18 and 70 years of age; and
- are willing to make an attempt to quit both cannabis and tobacco smoking.

Participants will be excluded for the following:

- expected to have unstable medication regimen during the study;
- currently receiving non-study behavioral treatment for cannabis use disorder or smoking;
- myocardial infarction in past six months;
- contraindication to NRT with no medical clearance;
- use of other forms of nicotine such as cigars, pipes, or chewing tobacco with unwillingness to stop use of these forms;
- current pregnancy;
- primary psychotic disorder or current manic episode;
- substance use disorder (other than mild alcohol use disorder, cannabis use disorder or nicotine use disorder) within the preceding three months; or
- current imprisonment or psychiatric hospitalization.

Recruitment

Participants will be recruited from primary care and substance use clinics at Duke University Medical Center (DUMC). Flyers and brochures will be placed in DUMC clinic areas, and may also be placed in community settings such as local restaurants and grocery stores. We will also advertise in local newspapers and online classified services such as www.craigslist.com. With permission from area

colleges and universities (and their respective IRBs where required), we will post flyers and brochures on area campuses. We will contact administrators and/or clinicians at local area community health centers, including Lincoln Community Health Center. Upon approval by the Durham Veterans Affairs (VA) Medical Center IRB, we will post flyers and brochures at that facility and its community-based outpatient clinics. Any flyer posted at the VA-owned facilities will include the following statement: "This is not VA research, will not be conducted by VA, has not been reviewed by VA's Institutional Review Board, and is not endorsed by VA. VA is not responsible for any costs incurred by a Veteran if the Veteran enters the study as a research subject. The announcement is being provided for information only."

Participants who find the study on clinicaltrials.gov and emails study staff will be sent an email to contact the study coordinator by telephone.

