Any participant who contacts by telephone the study coordinator or other study staff regarding the study will be provided more information, and will be interviewed using an IRB-approved telephone screening. We will retain the deidentified telephone screening information for all callers so that we can analyze data regarding telephone screen-outs in order to determine recruitment and inclusion/exclusion feasibility. Participants eligible at the phone screen will be scheduled for a screening visit. An email address will be collected from the participant to send directions and a parking pass for the screening location and send reminders of upcoming study appointments. If a participant does not have access to email or a printer, study staff will collect a mailing address to send directions and a parking pass via FedEx.

Prior to study entry, potential participants will complete a screening visit, including informed consent, diagnostic interview, a saliva sample to assess cannabis and a breath sample to assess CO level, symptom self-report measures, computerized impulsivity tasks, cannabis and smoking history, and sociodemographic data. Urine samples will also be used to screen for other illicit drug use. Because the study drugs are each Category C drugs, urine pregnancy tests will also be completed for women of childbearing potential. We have developed a short interview for female participants; this interview will help us determine which female participants must have a urine pregnancy test, and when the test should be done. Female participants of childbearing potential who are not pregnant must agree to use appropriate contraception during the course of the study, and to notify study staff if they become pregnant during the study. The participants' health information will be evaluated by the study physician, [name]., Ph.D., who will provide medical clearance to participate in the trial and use smoking cessation pharmacotherapy. [name] is an experienced psychiatrist and substance abuse researcher with a strong working relationship with the study team.

Procedures

All participants enrolled in the pilot project will receive TELE-HEALTH MOBILE CONTINGENCY MANAGEMENT (mCM) INTERVENTION, a proactive tele-health intervention that combines evidence-based telephone CBT for cannabis and smoking cessation, a tele-medicine clinic for access to nicotine replacement therapy (NRT) and intensive CM therapy administered *via* a smart phone-based

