Participants will receive training on mCM procedures, including use of the mCM app, CO monitor, and saliva kits, by study staff. If equipment is available for loan at the screening visit, participants will be given smartphones with the mCM app, a CO monitor, and numbered saliva kits. If equipment is not immediately available for loan, these things will be mailed to the study participant prior to his/her beginning the mCM monitoring phase of the study. After one week with no mCM activity, they will complete one week of baseline saliva assessments and CO monitoring to ensure that they are expert at using the mHealth technology and can troubleshoot any problems with the assistance of study staff. During the baseline week, participants will be reinforced for completing readings, regardless of abstinence. The baseline monitoring will be followed by four weeks of active mCM. Because an escalating, versus a fixed, reinforcement schedule has produced higher abstinence rates (Heil et al., 2008; Stoops et al., 2009), an escalating schedule will be used in this protocol (identical to our pilot studies). Participants will provide substance use data throughout the mCM phase simply by completing

their readings using the mCM app. After the practice week, monetary reinforcement will be contingent on abstinence from marijuana and tobacco smoking, operationally defined as THC readings that are < 40 ng/mL and CO readings that are < 6 ppm. Following the active CM treatment phase, two weeks of saliva tests and CO monitoring (without contingent reinforcement) will be completed so that we can assess the durability of treatment effects.

During the entire monitoring period, each evening, participants will answer a computerized daily diary (programmed by our mCM app developer) in which they'll be asked to report on cigarette smoking and cannabis use. Participants will be asked 1) if they smoked cigarettes; 2) how many cigarettes they smoked if applicable; 3) if they smoked marijuana and how many if applicable; 4) if they ingested marijuana and how much; and 5) if they vaped marijuana and how much. Participants will be paid \$1 per day for completing the diary.

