Standard cut-points of 10 ng/ml for cotinine and 50 ng/ml for THC9-carboxylic acid (THC-COOH) will be used to determine abstinence from nicotine and marijuana, respectively. Self-reported and bioverified prolonged abstinence from marijuana, tobacco smoking and dual abstinence at the 6-month follow-up will be the primary end-point. Secondary cannabis use and tobacco smoking outcomes will include 7-and 30-day point prevalence abstinence at each assessment, in which abstinence is defined as no cannabis or tobacco use in the prior 7 or 30 days, respectively. Outcomes will also include cannabis consumption patterns such as standard joints/week and proportion of days abstinent. Participants will also report number of cigarettes smoked each day and days of smoking abstinence. Collection of cannabis and tobacco smoking use data will allow for calculation of dual abstinence days and longest duration of dual abstinence.

Participant Reimbursement. Based on our experience in our previous clinical trials, we are including \$100 compensation for completing baseline, end of treatment, and 3- and 6-month follow-up assessments (up to \$400). To ensure that participants return the CO monitor and phone, we are providing postage-paid return mailers and adding a \$35 incentive for equipment return. Participants can earn up to \$1,442for full participation and abstinence for the mCM portion of the study. Total possible payment for participation is \$1,877.

Potential Risks

There is a risk of discomfort or distress in answering questions on the study measures. However, distress and discomfort related to questionnaire completion is usually temporary and well-tolerated. Risks also include discomfort related to quitting marijuana and quitting smoking. Symptoms of marijuana withdrawal may include headache, insomnia, sweating, night sweats, anxiety and/or depression, nightmares or vivid dreams, irritability, and cravings for use. Quitting smoking may cause difficulty concentrating, poor sleep, increased appetite, anxious or depressed mood, and craving for cigarettes.

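### The cannabis entry criterion has no recency element, so someone already off cannabis could enrol and meet the cannabis (not tobacco or dual) 7- and 30-day abstinence definitions at screening

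*Combined protocol and SAP*

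**What the plan says.** All references are to the combined protocol and SAP.

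- **Cannabis entry (Methods, Participants):** the participant must "report 40 or more days of cannabis use in the past 90 day". This is the only quantitative cannabis criterion.
- **Tobacco entry (same list):** the participant must "have smoked at least seven cigarettes in the past seven days". This carries recency.
- **Intention (same list):** participants qualify if they "are willing to make an attempt to quit both cannabis and tobacco smoking".
- **Size (Methods, Participants):** "Up to 10 participants with CUD and smoking will be enrolled, with a goal of 5 participants completing the intervention".
- **Screening sample (Recruitment):** the visit includes "a saliva sample to assess cannabis and a breath sample to assess CO level". No result is named as a condition of entry.
- **Reinforcement (mCM Procedures):** after the practice week, payment depends on abstinence from both substances, "operationally defined as THC readings that are < 40 ng/mL and CO readings that are < 6 ppm".
- **Outcomes (Follow-Up Visits):** "Secondary cannabis use and tobacco smoking outcomes will include 7-and 30-day point prevalence abstinence at each assessment", where "abstinence is defined as no cannabis or tobacco use in the prior 7 or 30 days, respectively". The primary endpoint is prolonged abstinence from cannabis, from tobacco and from both at 6 months.
- **Bioverification (mCM Procedures):** feasibility is judged on how well self-report, CO and saliva agree early in abstinence. If bedtime saliva tests disagree with self-report in weeks 1-2, monitoring becomes more frequent and less predictable.

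**The concern.** A count over 90 days says how much cannabis a person used, not whether they are still using it. The tobacco criterion shows that the plan can ask for current use; for cannabis it does not.

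Two results are exposed. The first is the cannabis abstinence proportion. A participant who was already abstinent at entry counts as a 7- or 30-day cannabis success without having changed their cannabis use. For prolonged cannabis abstinence at 6 months they start with a lead. There is no control arm, and Data Analyses describes no handling of cannabis abstinence at baseline.

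The second is the bioverification question, which is a stated purpose of the pilot. The Background argues for saliva testing because it avoids the urine washout around the quit date. Someone weeks past their last use cannot test that. If they stay off cannabis, they supply agreeing negatives: no use reported, no THC found. Agreement of that kind looks reassuring, says nothing about whether use would be detected, and makes the switch to more intensive testing less likely to be triggered.

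**Working it through.** The plan states no figure on this point and derives no sample size, so there is nothing to reproduce. The check is a count.

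**Inputs**
- Look-back window 90 days, minimum use days 40 (Methods, Participants).
- Outcome windows 7 and 30 days (Follow-Up Visits).
- Lead-in to quit day: one week with no monitoring, then one practice week, 7 + 7 = 14 days (mCM Procedures).
- Sample size: goal of 5 completers, at most 10 enrolled (Methods, Participants).
- Saliva detection window 6-12 hours (Background).

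**Step 1. Longest cannabis-free run before screening**
Longest run = window - use days = 90 - 40 = 50 days, reached when all 40 use days fall on days -90 to -51. Since 50 ≥ 30 and 50 ≥ 7, both cannabis definitions can be met at screening by self-report. If the person stays off cannabis, the run at quit day is 50 + 14 = 64 days.

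**Step 2. How far the gap extends beyond the extreme case**
A person with k use days can have d clear days at the end of the window whenever k ≤ 90 - d.

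| Outcome window d | Reported use days that still allow d clear days | Smallest count that would force use within d days |
|---|---|---|
| 7 days | 40 to 83 (90 - 7 = 83) | 84 |
| 30 days | 40 to 60 (90 - 30 = 60) | 61 |

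A threshold of 40 guarantees use in neither window. A count alone would need to be 84 of 90 to guarantee use in the last week, so raising the count is not a practical route.

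**Step 3. Which outcomes and payments are affected at screening**
- Cannabis 7- and 30-day abstinence: can be met.
- Tobacco 7- and 30-day abstinence: cannot be met, because at least seven cigarettes in the past seven days are required.
- Dual abstinence, or a literal reading of the definition as covering both substances together: cannot be met, for the same reason.
- Reinforcement rule: THC half met, CO half (below 6 ppm) not secured without stopping cigarettes.

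**Step 4. Weight of one participant**
1/5 = 20 percentage points among 5 completers; 1/10 = 10 percentage points among 10 enrolled.

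**Step 5. Whether another provision closes the gap**
- *Willingness to attempt to quit:* someone already in a quit attempt is willing.
- *Cannabis use disorder:* it appears in the sentence describing the population and the SCID-5 substance use section is administered, but neither is tied to recent use in the inclusion list.
- *Screening saliva:* collected with no entry threshold.
- *Screening urine:* described as a check for other illicit drugs.
- *Exclusion of people in other behavioural treatment:* removes some recent quitters, but not those who stopped unaided.

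None of these is a recency rule.

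**The case against.** The strongest reply is that a long-abstinent person is an unlikely enrollee. The study is described as one of people with cannabis use disorder, screening takes a diagnostic interview and a cannabis history, and an offer to help someone quit most naturally attracts people still using. Fifty days requires every use day to sit at the far end of the window. The practice week, with saliva tests and a daily diary, would also show such a person to be cannabis-free before quit day, and in a report on 5 to 10 people that could be stated openly. The analyses are mainly descriptive, the 7- and 30-day outcomes are secondary, and a single-arm pilot cannot attribute abstinence to treatment for anyone. Feasibility measures such as videos sent, sessions attended and attrition do not depend on recent cannabis use.

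Much of this stands, and it limits the size of the point. It does not remove it: the practice week comes after enrolment and no rule acts on what it shows, and the bioverification question does depend on people who were using until the quit date.

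Three stronger readings are tempting and are not supported.

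- *That such a person would collect the abstinence payments or count as a dual success without changing anything.* Payment requires CO below 6 ppm as well as THC below 40 ng/mL, and the cigarette criterion rules out dual abstinence at entry. The person must still stop smoking.
- *That passing the THC threshold before treatment is peculiar to this group.* With a 6-12 hour detection window, a current user who last used earlier than that may also test negative.
- *That the screening saliva sample already settles recent use, or could.* A negative result is compatible with use the day before.

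**Conclusion.** The concern holds in a limited form. The cannabis criterion lacks the recency element that the tobacco criterion has, and nothing else in the plan supplies it. A person with up to 50 cannabis-free days could be enrolled and already meet the cannabis 7- and 30-day definitions. Such a person also adds little to the test of whether monitoring detects use around the quit date.

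Fifty days is the worst case, not an expected value. How often anyone with even 7 or 30 clear days would apply cannot be estimated from the documents. The 20- and 10-point figures are the weight of any one participant at n = 5 and n = 10; they show how fragile the proportion is, not how large a bias to expect. The conclusion assumes that eligibility is applied as listed, and it concerns abstinence by self-report, because no screening result is fixed by the criteria.

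This is a cheap improvement worth making, not a flaw that undermines the pilot.

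**What to change.** Add one line to the inclusion list under Methods, Participants: *any self-reported cannabis use in the past 7 days*, matching the tobacco look-back. Ask it at the phone screen and again at the screening visit.

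Treat the screening saliva result as supporting information only. A positive supports recent use; a negative cannot refute use within 7 days, so it should not decide entry.

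Do not add an offer to re-screen applicants if their use resumes. With total payments of up to $1,877, that could reward an abstinent person for starting again.

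The cost is one line and one question on two existing contacts, with no new sample. An occasional applicant who has recently paused cannabis would not be enrolled. Recruitment already provides for keeping deidentified phone-screen data to study screen-outs, so losses at the phone screen would be visible.
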